## SH-RCT-LBP-US-01 Clinical Investigation Protocol

respectively. These trackers enable precise movement quantification, feeding the mobile app, which guides the patient through the session, providing video and audio instructions before each exercise, as well as real-time audio and video biofeedback during the exercise. On the other end, the clinical teams are allowed to remotely monitor results and prescribe/edit exercise sessions through a web-based portal.

The exercise component will follow the protocol outlined in **Annex 2**, which can however be adapted by the physical therapist to the specific needs of the participant. Participants will be asked to start with three 20 min sessions per week, building gradually to three 30 min sessions per week. Participants will not be excluded from the study in case of lower adherence. Participants in this group will be considered as dropouts if they: a) choose to abandon the study; b) do not engage in any exercise session for at least fourteen consecutive days.

The educational component will be delivered automatically through a smartphone app (available for iOS and Android), and will take the form of small educational texts that will be released periodically to the participant. This component is not mandatory per protocol, but metrics on user engagement will be measured.

The CBT program will take the form of a self-paced program consisting of written and pre-recorded audio materials. An email will be sent weekly by the physical therapist to the participant, during the 8 weeks of the program. Each email will contain an introductory text describing the objectives for that week, as well as a link to that week's audio session and a PDF attachment with self-guided exercises. The CBT component is not mandatory per protocol, but metrics on user engagement will be measured.

### 14.2 Conventional PT

Patients in this group will benefit from a 8-week program consisting of two 30 min face-to-face PT sessions per week in an outpatient clinic setting, for a total of 16 sessions. The program will follow the protocol outlined in **Annex 3**, which can however be adapted by the physical therapist

## SH-RCT-LBP-US-01 Clinical Investigation Protocol

will be considered as dropouts if they: a) choose to abandon the study; b) miss four consecutive scheduled PT sessions.

### 15. ASSESSMENTS AND SPECIFIC DATA COLLECTION

Patients will be assessed at baseline, 4 and 8 weeks. All questionnaires will be collected through the EDC system. These will need to be filled within 5 consecutive days. To promote compliance with this schedule, whenever the deadline is approaching, automatic email reminders will be sent to participants. Participants will be excluded from the study for protocol breach in case they don't fill in the assessment forms.

Regarding the **baseline assessment**, participants will be asked to complete the survey before the start of the program. This assessment will include all the information pertaining to the primary and secondary outcomes, as well as the following information:

- a) date of birth
- b) gender
- c) height & weight
- d) body mass index
- e) formal education (years of schooling)
- f) job type
- g) baseline physical activity level
- h) previous back surgery (> 3 months ago)
- i) risk factors: working status, smoking status

For the **4- and 8-week assessment**, participants will be required to complete the questionnaire within a 5-day window beginning at the start of week 4 and 8. These assessments will include all the information pertaining to the primary and secondary outcomes. Physical activity will be measured only at baseline and 8 week assessment.

For participants on the digital group, engagement and usage metrics of the educational and CBT components will also be collected automatically.

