### **13. ALLOCATION & BLINDING**

Patients will be randomly allocated to one of two groups, using random permuted blocks of 6. After eConsent collection, the investigator will enter the EDC portal and proceed with randomisation (also built into the EDC). Following randomisation, the investigator will contact the person responsible for the rehabilitation program in each group to allocate the participant to the respective study arm. Blinding of investigators and patients regarding allocation arm will not be possible, given the nature of the intervention. Analysis of study results will be performed by a statistician blinded to allocation groups.

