## 16. STATISTICAL ANALYSIS PLAN

To assess differences in clinical and demographic variables of the patients allocated to the two study groups, independent samples t test or Mann–Whitney U test will be used for quantitative variables. For categorical variables, Chi-square test or Fisher's exact test will be used.

Outcome analysis will be performed using both an intention to treat analysis and a per-protocol analysis.

The overall impact of the intervention on the primary and secondary outcomes will be assessed considering both the results at the 12-week assessment as well as change from baseline.

Differences between interventions will be evaluated using independent samples t test or Mann–Whitney U test. For non-normally distributed variables, the magnitude of the difference in the medians will be assessed using Hodges-Lehman estimator. Additionally, a repeated measures ANOVA will also be performed, with group as an independent factor and time as a within-subjects factor. When necessary, logarithmic transformation will be performed to obtain normally distributed variables. In all analysis, a significant level of 0.05 will be considered.

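### Section 15 removes from the study anyone who does not fill in the forms, so the intention-to-treat analysis promised in Section 16 can become an analysis of form completers

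*Combined protocol and SAP*

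**What the plan says.** Section 15 schedules assessments at baseline, week 4 and week 8. For the two follow-up assessments, "participants will be required to complete the questionnaire within a 5-day window beginning at the start of week 4 and 8". Automatic email reminders are planned. The consequence of not responding is then stated: "Participants will be excluded from the study for protocol breach in case they don't fill in the assessment forms".

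Section 16 says: "Outcome analysis will be performed using both an intention to treat analysis and a per-protocol analysis". It defines neither set. The listed methods are the t test or Mann–Whitney test, with a Hodges–Lehmann estimate for non-normal variables; in addition, "a repeated measures ANOVA will also be performed, with group as an independent factor and time as a within-subjects factor". It gives no imputation, missingness assumption or sensitivity analysis.

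Three other places bear on the point:

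- **Dropout rules.** Section 14 classes participants as dropouts if they abandon the study or, in the digital arm, "do not engage in any exercise session for at least fourteen consecutive days", or, in the conventional arm, "miss four consecutive scheduled PT sessions". For the digital arm, Section 14.1 adds that lower adherence does not lead to exclusion.
- **Timing of randomisation.** Section 13: "After eConsent collection, the investigator will enter the EDC portal and proceed with randomisation". Section 15 fixes the baseline form only relative to treatment: "participants will be asked to complete the survey before the start of the program".
- **Sample size.** Section 9 gives 102 individuals and mentions no allowance for loss.

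**The concern.** Returning a form happens after randomisation, in an open-label trial whose primary outcome is patient-reported. A rule that removes non-returners selects participants on something that treatment may influence. If return differs by arm and is related to how patients are doing, the comparison can be biased in either direction.

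The rule also acts on data collection. A participant removed at week 4 is not asked for the week-8 ODI, and no later analysis can recover a value that was never collected.

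The hypothesis in Section 6 is that the digital program does at least as well as conventional PT. For that claim, agreement between ITT and per-protocol results is a useful safeguard. If both sets contain only form completers, they are no longer distinct checks.

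**Working it through.** **1. Reading the text.** The exclusion is from the study, with no analysis set mentioned. Section 14.1 uses the same idea for low adherers in the digital arm, and there it plainly means study participation. The sentence follows directly on the three-visit schedule, so it naturally covers week 4. The Section 16 methods do not restore anyone: the t test and Mann–Whitney test use observed outcomes only, and standard repeated measures ANOVA uses only participants with every time point. Because randomisation may precede the baseline form, even a missed baseline form may be a post-randomisation loss.

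**2. The plan's own figure.** Inputs from Section 9: SD 17.83, difference 10, two-sided 0.05, power 80%; 1:1 allocation assumed. Normal approximation: 2 × (1.96 + 0.8416)² × 17.83² / 10² = 49.9, so 50 per arm. Noncentral t: 50.9, so 51 per arm and 102 in total, matching the plan. Power with all 102 analysed is 80.1%, so there is no reserve.

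**3. Loss added by the rule.** Let p be the assumed chance of missing each follow-up form. Without the rule, week-8 loss is p. With it, and independent misses, loss is 1 − (1 − p)².

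| p | Loss without rule (left of 102) | Loss with rule (left of 102) |
|---|---|---|
| 5% | 5% (97) | 9.8% (92) |
| 10% | 10% (92) | 19% (83) |
| 15% | 15% (87) | 28% (74) |

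At p = 10% with correlation 0.5 between the two misses, both are missed with probability 0.01 + 0.5 × 0.09 = 0.055. Loss is then 0.20 − 0.055 = 14.5% (87 left). With correlation 1, the rule adds nothing.

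**4. Bias with a true effect of 0.** If excluded participants average g points worse than completers in both arms, completers' means are too good by (loss rate × g). The bias is therefore g × (difference in loss rates), in favour of the arm that loses more. With g = 10 and 10% versus 20% loss: 10 × 0.10 = 1.0 point.

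A simulation used correlations of 0.5 with baseline and 0.7 between weeks 4 and 8. The log-odds of non-return rose by 0.25, 0.5 or 1 per SD of worse week-4 change. All of these are assumptions.

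| Loss by arm | Change-score bias | Raw week-8 bias | SE of change comparison | Type I error, change (nominal 5%) |
|---|---|---|---|---|
| Equal | 0.00 | – | – | – |
| 10% vs 20% | 0.30, 0.59, 1.02 | 0.08, 0.17, 0.29 | 3.84 | 5.1% to 5.8% |
| 10% vs 30% | 0.61, 1.16, 2.01 | 0.17, 0.32, 0.57 | 3.98 | 5.3% to 7.9% |

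The largest bias is 2.01 / 3.98 = 0.51 of a standard error.

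**5. What repairs it.** If half of the week-4 non-returners still supply week 8, the 10% versus 30% change-score bias falls to 0.23, 0.44, 0.76. Adjusting for baseline and week 4 brings it within 0.01 of 0, but needs week-4 scores that non-returners did not give. Adjusting for baseline alone leaves 0.39, 0.76, 1.34. Continued collection therefore matters, and a sensitivity analysis is still needed.

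**6. Power if 102 is the number randomised.** Raw week-8 scores: 80.1%, 78.0%, 75.8% and 70.8% with 102, 97, 92 and 82 analysed. The other analyses depend on the baseline/week-8 correlation r, which the documents do not give:

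| Analysis (SD used) | Loss | r = 0.3 | r = 0.5 | r = 0.7 |
|---|---|---|---|---|
| Change, 17.83 × √(2 − 2r) | 0% | 65.9% | 80.1% | 95.2% |
| Change | 20% | 56.4% | 70.8% | 90.0% |
| Baseline-adjusted, 17.83 × √(1 − r²), approximate | 0% | 83.7% | 90.0% | 97.5% |
| Baseline-adjusted | 20% | 74.9% | 82.6% | 94.0% |

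For change scores, loss itself costs about 5 to 10 percentage points; the rest of the spread is the correlation.

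**The case against.** The sponsor may have meant the rule for the per-protocol set only. It speaks of a protocol breach, a per-protocol analysis is planned, and the text does not say that one missed form ends follow-up. That reading is possible, but no section states it, and an investigator following Section 15 has no reason to apply it.

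The assumed bias is modest: at most 2.0 points against the 10-point minimal clinically important change (MCIC) in Section 9, and 0 with equal loss. This stands.

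The evidence for unequal loss is thin. Section 1 says that almost half of patients sent to PT give up after 4 sessions, and Section 2 credits digital programs with high engagement. The latter concerns knee and hip arthroplasty, and both concern sessions rather than forms. They show that unequal loss is plausible, not how large it would be. Reminders, and drop-out rates as a secondary outcome, would reduce or reveal unequal loss but would not correct for it.

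The consent form (Annex 1) was not available for this check, and Section 14.2 is broken mid-sentence in the copy used. Either could say what happens to collected data or whether conventional-arm dropouts still receive forms. Those two remarks are therefore tentative; the Section 15 rule does not depend on them.

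Finally, the week-8 t test does not need week-4 data, and the ANOVA is only additional. That is true of the tests, but the rule can prevent the week-8 value from being collected.

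**Conclusion.** The concern holds. As written, Section 15 can reduce the promised ITT analysis to form completers, and nothing in Section 16 prevents or repairs this.

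The size is unknown. Under the assumptions shown, the rule adds anything from no loss to roughly a doubling of week-8 loss. Change-score bias runs from 0 with equal loss to 2.0 points at 10% versus 30% loss with the steepest dependence on outcome. The direction depends on which arm loses more and on whether non-returners are doing worse or better.

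The conclusion that the text must change does not rest on these figures. It rests on the conflict between the rule and the analysis the plan promises, and on the loss of primary-outcome data that cannot be recovered afterwards.

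**What to change.** **Section 15.** Replace the sentence with: *A form not returned is recorded as missing; the participant stays in the study for later assessments and in the ITT set.* Confine any form-completion rule to the per-protocol set. Record forms returned after the 5-day window with their date and use them in the ITT analysis. Keep requesting the week-4 and week-8 forms from participants classed as dropouts under Section 14, unless they withdraw consent. Say whether the baseline form is due before randomisation.

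**Section 16.** Define ITT as all randomised participants, as allocated. Analyse ODI in that set with a method that uses all available baseline, week-4 and week-8 values (a likelihood-based mixed model or multiple imputation), keeping the listed tests as supportive. Add a delta-type sensitivity analysis, by arm, with the shifts fixed in advance. Other principled missing-data methods would also serve; the need is to name one beforehand.

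**Section 9.** Say whether 102 is the number randomised or the number evaluable. If randomised, state that 80.1% assumes no loss; that raw week-8 power is about 78%, 76% and 71% at 5%, 10% and 20% loss; and that change-score or baseline-adjusted power depends on an unstated correlation and may be higher or lower.

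**Cost.** Protocol and SAP wording, reminders to non-responders and dropouts up to week 8, slightly more analysis, and possibly a less favourable stated power. No added patients or visits.

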## SH-RCT-LBP-US-01 Clinical Investigation Protocol

Additionally, the following activity log will be collected from patient's Electronic medical records and time stamps, as well as paper survey (or, in the case of the digital group, sent to the study coordinator via email, with the participant identified only by the study ID), to be entered into EDC portal by study coordinator:

1. Face-to-face visits registry (dates, times and duration)
2. Remote sessions registry (dates, times and duration)
3. Total time spent on remote monitoring of the patient (digital group only)

When applicable, **adverse events** reporting will also be made through this portal and annexed to patient's file (beginning date, resolution date (if applicable), resolution state, severity, description).

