## **9. SAMPLE SIZE ESTIMATION**

Sample size estimation calculations were performed taking into consideration the primary outcome measure – The Oswestry Disability Index (ODI). In the absence of similar studies, the calculations were made considering the study by Stankovic et al. (2012). This was a large study (n=160 patients), which compared two different rehabilitation protocols for CLBP and which used the same primary outcome as the present study. In this study, the standard deviation of the ODI at baseline was 17.83 points. A Minimal Clinically Important Change (MCIC) of 10 points was considered, based on the study by Ostelo et al. Considering a power of 80% and a two-sided 0.05 significance level, 102 individuals will be necessary to detect a 10-point difference between the two groups.

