## 17. RISKS AND BENEFITS

## SH-RCT-LBP-US-01 Clinical Investigation Protocol

Participants in this clinical study will be allocated to one of two treatment groups. In any case, they will be receiving an evidence-based treatment program tailored to their condition, overseen by physicians and physical therapists.

Participants in the digital care program will be performing the exercise component using a certified medical device for its intended purpose. Therefore, participants are not running additional risks by participating in this study.

Exercise programs can, however, be associated with temporary pain or discomfort. In the digital care group, pain and fatigue scores will be asked at the end of each session, and this information is relayed to the physical therapist assigned to the participant, who will contact the patient in case of excessive pain or fatigue. In the conventional PT group, sessions will be performed under direct supervision from a physical therapist. In any case, both participants and physical therapists will be instructed to contact the study investigators in case of an adverse event.

As to the benefits, by participating in this study, participants may experience reduction in pain, improvement in function, mood and general well-being. However, the effects may vary from person to person, and therefore substantial improvements cannot be guaranteed.

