**ANNEX 3- CONVENTIONAL THERAPEUTIC EXERCISE PROTOCOL**

Conventional Physical Therapy will be individualized according to the patient's symptoms and baseline physical capabilities. The therapy will include the following components

1) Therapeutic Exercises

These exercises will be initiated by the physical therapist, with instruction to continue at home. Patient may progress along intensity level as tolerated under the guidance of the physical therapist. Additional sports/activity specific exercises maybe included and not listed below.

Conventional PT Exercises	Low Intensity	Medium Intensity	High Intensity
Dead Bugs (Supported Arm)	2-4 sets of 2 min set		
Dead Bugs (Unsupported Arm)		3-5 sets of 3 min Rep (alternating)	3-5 sets of 5 min Rep with weight in hands(alternating)
Partial sit up	Arm Reaching between the thighs 10 reps x 2 sets	Arm crossed at chest 10 rep x 3 sets	Hand behind head 20 rep x 3 sets
Bridging	Both foot on the floor 10 reps x 2-3 sets	Single Leg on the floor 20 reps x 2-4 sets	Balance on stability ball 20 reps x 5 sets
Plank (Forearm)	10 second hold 3 sets	30 second hold 3 sets	60 second hold 3 sets
Prone	Opposite Arm/leg lift 10 reps x 1-2 sets	Opposite Arm/leg lift (On balance ball) 10 reps x 1-2 sets	Opposite Arm/leg lift (On balance ball) 20 reps x 1-2 sets
Quadruped	Opposite Arm/leg lift 10 reps x 1-2 sets	Opposite Arm and leg lift 10 reps x 1-2 sets	Opposite Arm and leg lift (with weight in hand and ankle weight) 10 reps x 1-2 sets
Side plank (From Knee)	10 second hold 3 sets	30 second hold 3 sets	60 second hold 3 sets
Wall Slide (Or Ball slide against wall)	45 degree 10 -20 reps	90 degree 10 reps with 30 sec hold	90 degree, with weights and arm extended 10 reps with 30 sec hold

- 2) **Manual Therapy:** During the patient's physical therapy treatment manual therapy may be applied by skilled physical therapists as necessary for the patient's condition.
  - Soft tissue mobilization
  - Joint mobilization/manipulation
  - Myofascial release
  - Trigger point dry needling
  - Cupping
- 3) **Active and Passive Stretches**

All stretches maybe completed by patient alone or be assisted/augmented by the physical therapist

  - Hip flexor/quad stretch
  - Hamstring stretch
  - Glute/piriformis stretch
  - QL stretch
- 4) **Range of Motion exercises**

These will be both active and passive under the assistance of the physical therapists and will be progress under the instruction by the physical therapist.

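### Adverse event ascertainment depends on arm and on continued sessions, and the recorded fields omit seriousness and relatedness

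*Combined protocol and SAP*

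**What the plan says.** - **Fields.** Section 15 enters adverse events in the EDC portal, when they occur, as "beginning date, resolution date (if applicable), resolution state, severity, description".
- **Monitoring, digital arm.** Section 17 collects pain and fatigue scores at the end of each session. They go to the assigned therapist, who contacts the participant if they are too high.
- **Monitoring, conventional arm.** Section 17 states: "In the conventional PT group, sessions will be performed under direct supervision from a physical therapist". No score is mentioned. Annex 3 says of the same programme: "These exercises will be initiated by the physical therapist, with instruction to continue at home".
- **Common route.** Section 17 tells participants and therapists in both arms to contact the investigators if an adverse event occurs.
- **Common forms.** Of the 4- and 8-week questionnaires, Section 15 says: "These assessments will include all the information pertaining to the primary and secondary outcomes". None of the outcomes in Section 8 is an adverse event. Participants who do not return the forms are excluded from the study.
- **Dropout.** A digital participant is a dropout on leaving the study or if they "do not engage in any exercise session for at least fourteen consecutive days" (Section 14.1). The conventional rule is leaving, or missing four scheduled sessions in a row (Section 14.2). Neither section asks for a reason.
- **Analysis.** Section 16 does not mention adverse events.

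**The concern.** What a participant is asked about symptoms, and by whom, depends on the arm, and in both arms it depends on sessions continuing. A difference in event counts could then reflect how events were found as well as how many occurred. Someone who stops because of an exercise-related problem leaves the session-based monitoring. Section 8.2(g) counts drop-out as an engagement measure, so that person may appear in the results only as disengaged.

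The field list raises a separate problem. Severity describes how intense an event was; it does not say whether the event was serious or what caused it. The digital arm uses a medical device, and Annex 3 allows manipulation, dry needling, cupping and traction. A reader of the trial report would expect a statement on serious events and on events related to either treatment. The listed fields do not supply the data for one.

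**Working it through.** **1. The plan's own figure.** Section 9 gives: "Considering a power of 80% and a two-sided 0.05 significance level, 102 individuals will be necessary", from "A Minimal Clinically Important Change (MCIC) of 10 points was considered" and "the standard deviation of the ODI at baseline was 17.83 points". The normal formula is n per arm = 2 × (1.960 + 0.842)² × 17.83² / 10² = 49.9, so 50 per arm and 100 in total. The t-test version gives 50.88, so 51 per arm and 102 in total. The figure is reproduced. It matters here only as a denominator: 51 per arm, assuming 1:1 allocation, which Section 13 does not state.

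**2. Sources of event information, side by side.**

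| Source | Digital | Conventional |
|---|---|---|
| Structured score after each session | Yes | None stated |
| Direct observation | No; remote monitoring | 16 supervised visits; home exercise unobserved |
| Spontaneous report to investigators | Yes | Yes |
| Adverse event item at weeks 4 and 8 | None listed | None listed |
| Reason recorded at dropout | None stated | None stated |

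The first two rows differ by arm and stop when sessions stop. The third is common but unsolicited. The last two would give equal ascertainment, and they are empty.

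**3. Dropout rules.** Digital: 14 days. Conventional: 4 missed sessions at 2 per week = 2 weeks. The rules match in length and do not themselves create an imbalance. The gap is the unrecorded reason, in both arms.

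**4. What unequal capture can do.** The documents give no event rate and no capture rate, so these are assumptions and not estimates. Observed rate = true rate × proportion captured. With equal true rates and capture of 90% in one arm and 50% in the other:
- true 10%: 9% v 5%, a spurious 4 points
- true 20%: 18% v 10%, a spurious 8 points
- true 30%: 27% v 15%, a spurious 12 points

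Exchanging the capture rates reverses each sign. A real difference can also vanish: true rates of 20% v 10% with capture of 45% v 90% give 0.20 × 0.45 = 9% and 0.10 × 0.90 = 9%.

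**5. What the trial could show with full capture.** For 20% v 10% with 51 per arm, the standard error is √(2 × 0.15 × 0.85/51) = 0.071 under no difference and √((0.16 + 0.09)/51) = 0.070 under the alternative. Then z = (0.10 − 1.96 × 0.071)/0.070 = −0.55, so power is 29%. Zero events in 51 gives a one-sided 95% upper limit of 1 − 0.05^(1/51) = 5.7%, valid only if every event is captured.

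**The case against.** The strongest reply is that the formal reporting route is already the same. Both arms get one instruction, use one portal and have one field list; the session score is monitoring of exercise tolerance that feeds this route. Conventional participants see a therapist twice a week, who progresses them as tolerated and can hardly do so without asking about symptoms. Digital participants have an assigned therapist, uploaded session results and a weekly email. Disability, pain and medication are asked identically at weeks 4 and 8. Harms are not in the objective, hypothesis or outcomes, and the trial is too small to test them.

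Much of this stands, and it rules out three stronger readings that a reader might infer:
- *That events in people who stop are missed.* The documents do not show this. Those participants have still been told to report, and their pain is asked about if they return the forms. They are at risk of under-reporting.
- *That harms cannot be compared at all, or that the digital arm will record more.* Events can be tabulated by arm. Session scores may raise digital capture, and face-to-face contact may raise conventional capture, so the direction is unknown.
- *That conventional participants are never asked, so digital prompts can be tallied against none.* That argues from silence and gives 16 visits no weight. The digital tally is itself uncertain: Section 14.1 describes three sessions a week and the Annex 2 headings say daily, which must be reconciled.

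The reply does not supply the missing items. A 24-hour pain score does not identify an event, its cause or why sessions ended, and a common instruction to volunteer events is not equal solicitation. The text of Section 14.2 is broken and the consent form was not available, so statements about what is absent apply to the text reviewed.

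**Conclusion.** The point holds as a weakness in how harms are collected, and it should be corrected. Following the plan exactly would give a by-arm tabulation open to ascertainment bias of unknown direction. It would leave events that lead to stopping at risk of under-reporting, and individual events could not be classified from the listed fields as serious or as related to the device or treatment. The first two conclusions rest on the stated monitoring arrangements; the third rests on the field list alone.

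The size of the bias cannot be stated. The 4- to 12-point range in the working depends entirely on assumed event and capture rates. The primary disability result is not affected. Because power is low even with complete capture, the aim should be an unbiased descriptive account and not a between-arm test.

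**What to change.** In Section 15:
1. Add one identical question to the existing 4- and 8-week EDC forms in both arms, covering any new or worsened health problem and whether it limited or stopped sessions. Send it also to participants who have stopped sessions.
2. When either arm's dropout rule is met, have the coordinator ask the same question and record the reason.
3. Add seriousness and investigator-judged relation to the device or treatment component to the adverse event fields.
4. State that events will be summarised by arm descriptively from these common sources, with the digital session scores reported separately.

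The cost is one question on two existing forms, two fields and one contact per dropout. The downside is more non-serious events recorded in both arms and a little coordinator time. The 8-week form opens at the start of week 8, so events after it is completed would still rely on spontaneous reporting, equally in both arms. Sample size and treatment do not change. The items should be in place before data collection, because reasons for stopping and causality judgements are hard to recover later.
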